Project proposal for the PhD project:

Psychiatric comorbidity in Back Pain Disorders
– Risk, treatment and pharmaco-epidemiological analysis

Applicant

[name], MscPH

Medical Research Department, Spine Centre of Southern Denmark

Last update: 29 of January 2019

Introduction

Chronic pain is a common health problem negatively affecting sleep, work ability and socialization¹⁻⁴. Chronic pain also increases morbidity, mortality and health care costs and has a direct and severe impact on the quality of life^{3 5-8}. The prevalence of chronic pain is up to 46,5% in the general population⁵. Musculoskeletal back and neck pain are one of the most common pain conditions^{2 9} with a lifetime prevalence of low back pain in the range of 51%-84%⁶. Variation in prevalence estimates can be explained by a difference in the definition of pain, research methodologies and differences in study samples¹⁰.

Several different diagnostic classifications systems for back pain disorders (BPD) exist, but most frequently these are divided into specific and non-specific BPD¹¹. This study chooses to establish two subgroups for specific BPD based on the presumed cause of illness and available treatment options and one group for unspecified BPD (UBD). The specific subgroups consists of inflammatory back diseases (IBD) and degenerative back diseases (DBD)¹².

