Psychiatric comorbidity will be defined as the presence of any of the following diagnosis, according to ICD-10 classification³⁰, obtained from the National Patient Registry – Psychiatry (NPD-Psych), covering all inpatient and outpatient psychiatric services in Denmark in the time period 1th January 2007 to 31th December 2017: Organic, including symptomatic, mental disorders (F00-DF09), Mental and behavioral disorders due to psychoactive substance use (F10-F19), Schizophrenia, schizotypal and delusional disorders (F20-F29), Mood [affective] disorders (F30-F39), Neurotic, stress-related and somatoform disorders (F40-F48), Behavioral syndromes associated with physiological disturbances and physical factors (F50-F59), Disorders of adult personality and behavior (F60-F69), Mental retardation (F70-F79), Disorders of psychological development (F80-F89), Behavioral and emotional disorders with onset usually occurring in childhood and adolescence (F90-F98) and, Unspecified mental disorder (F99). To qualify as a psychiatric comorbidity to back pain disorder, we define that the psychiatric diagnosis must be given no earlier than three years prior to back pain disorder diagnosis and no later than three years after.

Study 1) Prevalence of psychiatric comorbidity in back pain disorders

Psychiatric comorbidity in Back Pain Disorders
Risk, treatment and pharmaco-epidemiological analysis

Aim: 1) To estimate prevalence of psychiatric comorbidity in patients with BPD compared to patients without BPD and 2) To estimate prevalence of psychiatric comorbidity in patients with unspecific back pain (UBP) compared to the background population and to patients with a specific back pain (SBP) in a Danish nationwide cohort from 2010-2014.

Hypothesis: 1) There is a higher risk of psychiatric comorbidity in BPD patients compared to the background population and 2) UBP patients have a higher risk of psychiatric comorbidity compared to patients with specific BPD.

Design: The study will be a nationwide register-based matched cohort study.

Procedure: Selected BPD patients with the following diagnosis will be identified via the DNPR: Spondylopathies DM45-49, Other dorsopathies DM 50-54 and Segmental and somatic dysfunction DM99. Each patient will be matched 1:5 on age and sex with patients without back disorders by random at Statistics Denmark³⁸. The selection of diagnosis is to be able to match the population with non-BPD patients in the Danish registries.

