Information on somatic comorbidity for calculation of Charlson Comorbidity index³⁹ (CCI) at time of BPD diagnosis, will be retrieved from the DNPR. Data on psychiatric comorbidity will be identified using NPD-Psych. Information on marital status, vital status, and immigration status will be retrieved from the Civil Registration System (CPR)³⁵. Patients that are not alive or have emigrated within three years after BPD diagnosis are considered lost to follow-up and excluded from the cohort. Descriptive data on the socioeconomic status, education level and equivalent available income will be retrieved from Statistics Denmark³⁸. All data comprising each variable will be retrieved from 1th of January 2007 to 31th of December 2017 (three years before and after study period).

Measures of outcome: Primary outcome is to estimate prevalence of psychiatric comorbidity in patients with BPD compared to the Danish background population. Secondary outcome is to estimate prevalence of psychiatric comorbidity stratified by type of BPD (SBP UBP) compared to the Danish background population. We will use a presence of psychiatric comorbidity as outcome.

Statistics: We will use Fisher's exact test and t-test to compare baseline characteristics with 95% confidence intervals (CI) and p-values. Crude risks of psychiatric comorbidity will be calculated and logistic regression model will be used, to investigate differences between the distribution of risk in BPD patients and the background population. A logistic regression model will also be used to investigate differences between the distribution of psychiatric comorbidity in the IBD, DBD and UBP group compared to the background population. The logistic regressions will be reported using 95% CI and adjusted for the following confounders: age, sex, equivalent available income, educational level, CCI, marital status.

Study 2) The effect of psychiatric comorbidity on type of treatment for BPD

Aim: 1) To investigate whether treatment of BPD in patients with psychiatric comorbidity differ from treatment of patients with BPD without psychiatric comorbidity; 2) To investigate whether treatment of BPD differs in the following subgroups: a) specific BPD and no psychiatric comorbidity; b) specific BPD with psychiatric comorbidity; c) unspecific BPD with no psychiatric comorbidity; d) unspecific BPD with psychiatric comorbidity. Investigation will be performed in a nationwide Danish cohort in 2010-2014.

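### The second hypotheses of Studies 1 and 2 have no matching adjusted estimate: Study 1 specifies no unspecific-versus-specific odds ratio, and Study 2 no estimate by back pain type or across its four groups

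*Combined protocol and SAP*

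**What the plan says.** **Definitions.** The Introduction divides back pain disorders (BPD) into an unspecified group and two specific ones: "The specific subgroups consists of inflammatory back diseases (IBD) and degenerative back diseases (DBD").

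**Study 1.** The second aim sets UBP against two comparators: "compared to the background population and to patients with a specific back pain (SBP"). The second hypothesis is directional: "UBP patients have a higher risk of psychiatric comorbidity compared to patients with specific BPD". Under Measures of outcome, the secondary outcome is prevalence "stratified by type of BPD (SBP UBP) compared to the Danish background population". Under Statistics, "Crude risks of psychiatric comorbidity will be calculated", and a logistic model addresses the "distribution of psychiatric comorbidity in the IBD, DBD and UBP group compared to the background population", adjusted for age, sex, income, education, Charlson index and marital status. Matching is described as "Each patient will be matched 1:5 on age and sex with patients without back disorders".

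**Study 2.** The second aim lists four groups. Groups a and b are specific BPD without and with comorbidity, followed by "c) unspecific BPD with no psychiatric comorbidity; d) unspecific BPD with psychiatric comorbidity". The second hypothesis is that comorbidity influences treatment within BPD subgroups. Statistics gives one logistic model per treatment type, contrasting patients with and without comorbidity. BPD type (three levels) is in the list of confounders. The design paragraph also mentions a sub-analysis restricted to patients with comorbidity, with no model and no link to an aim.

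**Study 3**, by contrast, fits its first Cox analysis separately in specific and unspecific BPD.

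**The concern.** Each second hypothesis names a contrast that the Statistics text does not estimate.

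In Study 1 the specific-BPD comparator appears in the aim and the hypothesis. It is gone from both the secondary outcome and the model, where the background population is the only reference. Inflammatory and degenerative disease enter separately, so no pooled specific group is modelled either. Showing that UBP exceeds background does not show that it exceeds specific BPD. The crude prevalences of the two types may appear side by side, but they are unadjusted. The matching does not help, because it pairs BPD patients with non-BPD comparators and does not balance UBP against specific BPD.

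In Study 2, entering BPD type as a confounder forces a common comorbidity effect across types. The second hypothesis asks about effects within types, which needs stratification, an interaction or a four-level group variable. None is stated. The sub-analysis holds only groups b and d. It could compare those two, but without non-comorbid patients it cannot estimate a comorbidity effect.

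If this stays open, the reference group, the pooling of the specific types and the interaction model would be chosen after the data are seen.

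**Working it through.** **Inputs.** The documents state no cohort size, prevalence, BPD mix or treatment rate, so there is no planned figure to reproduce. Only the 1:5 matching comes from the plan; every other input is an assumption. The results show what is possible, not what is likely.

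**1. Study 1: do ORs versus background settle the second hypothesis?** Assume 20,000 BPD patients, 50% UBP (10,000 per type), background prevalence 3%, and each type against its own 50,000 comparators. A group with odds ratio OR has risk p = OR·(0.03/0.97) / [1 + OR·(0.03/0.97)]. This gives 5.27% for OR 1.8, 4.43% for 1.5 and 4.86% for 1.65. The variance of a log OR is the sum of 1/[n·p·(1−p)] over the two groups.

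| Specific vs background | UBP vs background | UBP vs specific |
|---|---|---|
| 1.80 (1.63–1.99) | 1.50 (1.35–1.67) | 1.5/1.8 = 0.83 (0.73–0.95) |
| 1.50 (1.35–1.67) | 1.80 (1.63–1.99) | 1.8/1.5 = 1.20 (1.05–1.37) |
| 1.65 (1.49–1.83) | 1.65 (1.49–1.83) | 1.00 (0.88–1.14) |

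For the first row, the contrast has SE = √(1/[10,000 × 0.0527 × 0.9473] + 1/[10,000 × 0.0443 × 0.9557]) = 0.066.

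Both ORs versus background are clearly above 1 in every row, whether the hypothesis is contradicted, supported or null. The same OR pairs were run over 20,000 or 200,000 patients, 3% or 10% prevalence and 20%, 50% or 80% UBP. The lowest confidence limit versus background was 1.26, or 1.28 if the whole comparator pool serves each type.

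**2. Study 1: do crude prevalences settle it?** Assume risk is 10% in younger and 4% in older patients regardless of type, with 70% of UBP and 40% of specific patients younger.

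- UBP: 0.7 × 0.10 + 0.3 × 0.04 = 0.082
- Specific: 0.4 × 0.10 + 0.6 × 0.04 = 0.064
- Crude OR = (0.082/0.918)/(0.064/0.936) = 1.31, while the age-adjusted OR is 1.00

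With 60%/50% younger the crude OR is 1.09; with 40%/70% it is 0.77.

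**3. Study 2: what does the single OR show?** Assume 200,000 patients, 50% UBP, 12% comorbid and a 7% treatment rate without comorbidity in both types. Group sizes are 88,000 (a), 12,000 (b), 88,000 (c) and 12,000 (d). Within-type comorbidity ORs are 0.80 in specific and 1.25 in unspecific BPD. A logistic model with comorbidity and BPD type as main effects was fitted to the expected counts.

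| Estimate | OR (95% CI) | Given by the stated model? |
|---|---|---|
| Comorbidity, single OR | 1.02 (0.97–1.08) | Yes |
| Comorbidity within specific (b vs a) | 0.80 (0.74–0.87) | No |
| Comorbidity within unspecific (d vs c) | 1.25 (1.17–1.34) | No |
| a vs c | 1.00 (0.96–1.04) | No |
| d vs b | 1.25/0.80 = 1.56 (1.41–1.73) | No |

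Swapping the two within-type ORs leaves the single OR at 1.02. At 20% UBP it is 0.89 (0.84–0.94) and at 80% UBP 1.16 (1.10–1.22), reversed if the ORs are swapped. A separate check used within-type ORs of 0.70 and 1.30, a 10% baseline, 10% comorbidity and equal type sizes. It gave a single OR of 0.99.

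**The case against.** The strongest objection is to the Study 1 half. The text can be read as one adjusted model with inflammatory, degenerative, unspecific and background groups. Adjusted UBP-versus-inflammatory and UBP-versus-degenerative contrasts are then differences of planned coefficients, and a reader can divide two reported ORs, as the first table does. On that reading the analysis is present but not named, and the crude-prevalence example matters less because adjusted ORs would stand beside it.

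Part of this stands: the point estimates against each specific type would be recoverable. But the plan does not say that it is one model, does not name the contrast, and gives no rule for combining the two specific types, which the hypothesis treats as one group. Nor can the contrast's confidence interval be taken from the two reported intervals. With assumed risks of 4% (background), 6% (specific) and 7% (UBP), equal type sizes and a shared 1:5 background, treating the two ORs as independent makes the standard error about 7.6% too large.

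For Study 2, it is fair that a single OR near 1 needs effects in opposite directions and a balanced mix, and that the documents give no reason to expect this. At 20% or 80% UBP the single OR excludes 1. However, it still gives no estimate for either type, and that is what the hypothesis asks about. It is also true that the aim names no pairwise contrasts, so a different stated set covering the aim would be acceptable.

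Finally, this is a PhD proposal. It is nonetheless the only analysis plan supplied, and it has numbered hypotheses, named models and confounder lists.

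**Conclusion.** The concern holds and should be fixed before analysis. That the stated models do not deliver the contrasts in the second hypotheses of Studies 1 and 2 follows from the text alone and rests on no assumed number. In Study 1 the contrasts with each specific type may be derivable, but no pooled, adjusted UBP-versus-specific OR with its interval is specified. In Study 2 no within-type or four-group estimate is specified.

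How much this would change the conclusions cannot be measured from the documents. The figures above establish only that the planned outputs are compatible with opposite answers to both hypotheses. The first hypotheses of both studies are untouched.

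**What to change.** **Study 1.** Name the adjusted OR with 95% CI for UBP versus specific BPD, with inflammatory and degenerative disease pooled, as the analysis of the second hypothesis. It can come from a model within BPD patients or as a defined contrast of the group model; state which.

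**Study 2.** For each treatment type, fit a model in all BPD patients with the four groups a–d, which is equivalent to comorbidity by specific/unspecific type. Report adjusted ORs with 95% CIs for comorbidity within specific BPD (b vs a) and within unspecific BPD (d vs c). Add the between-type contrasts a vs c and b vs d. Test the interaction if a claim that the effects differ between types is to be made. State which aim the sub-analysis in comorbid patients serves.

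**Cost.** Revised wording, one contrast in Study 1 and four per treatment type in Study 2. The drawback is more estimates to report per outcome. All variables are already being retrieved.

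### Study 1 adjusts for covariates measured at BPD diagnosis, or at no stated date, although its outcome window opens three years earlier, so the adjusted odds ratios may condition on consequences of the outcome

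*Combined protocol and SAP*

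**What the plan says.** Below, the index date is the date of BPD diagnosis, which falls in 2010-2014.

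- **Outcome window.** The section Setting and study population requires that "the psychiatric diagnosis must be given no earlier than three years prior to back pain disorder diagnosis and no later than three years after". The Study 1 outcome paragraph states: "We will use a presence of psychiatric comorbidity as outcome". Diagnoses before and after the index date are pooled.
- **CCI.** The Study 1 Procedure says that information for the "Charlson Comorbidity index³⁹ (CCI) at time of BPD diagnosis, will be retrieved from the DNPR". It gives no corresponding date for matched controls, who have no BPD diagnosis.
- **Income, education, marital status.** Only the source registers are named. For the first two, "Descriptive data on the socioeconomic status, education level and equivalent available income will be retrieved from Statistics Denmark"; marital status comes from the Civil Registration System. The only time reference is a common range: "All data comprising each variable will be retrieved from 1th of January 2007 to 31th of December 2017".
- **Model.** Study 1 Statistics plans crude risks, then logistic models for BPD overall and for the IBD, DBD and UBP groups against the background population, "adjusted for the following confounders: age, sex, equivalent available income, educational level, CCI, marital status".
- **Before/after split.** The Study 2 Procedure classifies psychiatric diagnoses as prior to or after BPD diagnosis. Study 1 has no such split, no earlier covariate date, and no analysis without these covariates.

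**The concern.** A confounder should be fixed before the outcome can occur. Taking covariates at the index date normally achieves that, but here half of the six-year outcome window lies before the index date. Even on the natural reading, with everything measured at index, the covariates follow every pre-index psychiatric diagnosis. If some values come from later years, which the retrieval range permits, they can follow post-index diagnoses too.

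Psychiatric illness can plausibly change income and marital status. So can a back disorder that was present before its hospital diagnosis. Where both have acted, the covariate is a common consequence of exposure and outcome, and adjusting for it distorts the association between them. At stake are the adjusted OR for BPD against the background population and the subgroup ORs, which the plan would report as confounder-adjusted. In a nationwide cohort matched 1:5 the confidence intervals are likely to be narrow, and they would not reflect a systematic shift of this kind.

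**Working it through.** The plan states no prevalence or effect size, so there is no figure to reproduce. The check has two parts.

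**1. Dates (from the plan).** Window opening = index date minus 3 years; window close = index date plus 3 years; retrieval starts 1 January 2007.

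| Index date | Window opens | Window closes | Retrieved data before opening |
|---|---|---|---|
| 1 Jan 2010 | 1 Jan 2007 | 1 Jan 2013 | 0.0 years |
| 1 Jul 2012 | 1 Jul 2009 | 1 Jul 2015 | 2.5 years |
| 31 Dec 2014 | 31 Dec 2011 | 31 Dec 2017 | 5.0 years |

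In every case CCI is fixed three years after the window opens.

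**2. Possible size (all inputs assumed).** Take one binary covariate, such as low income, present in 20% of people with neither condition. The true BPD-psychiatric OR is 2.00, with no confounding. Psychiatric disorder raises the covariate with OR 3, BPD raises it with OR b, and there is no interaction. Write P(by) for the covariate's probability given BPD (b = 0/1) and psychiatric disorder (y = 0/1). If every psychiatric diagnosis precedes the covariate:

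Adjusted OR = 2.00 × P11 × P00 / (P10 × P01)

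The reference odds are 0.20/0.80 = 0.25, so P00 = 0.20. For psychiatric disorder only, the odds are 0.25 × 3 = 0.75, so P01 = 0.4286.

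- BPD OR 1.5: P10 = 0.2727, P11 = 0.5294. Factor = 0.5294 × 0.20 / (0.2727 × 0.4286) = 0.906, so OR = 1.81.
- BPD OR 2: P10 = 0.3333, P11 = 0.60. Factor = 0.60 × 0.20 / (0.3333 × 0.4286) = 0.84, so OR = 1.68.
- BPD OR 1.2: P10 = 0.2308, P11 = 0.4737. Factor = 0.958, so OR = 1.92.
- BPD OR 1.1: P10 = 0.2157, P11 = 0.4521. Factor = 0.978, so OR = 1.96.
- BPD OR 1.0: P10 = P00 and P11 = P01. Factor = 1, so OR = 2.00.

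The factor is the same in people with and without the covariate.

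These values overstate the effect on the planned model, because only some diagnoses precede the index date. A large-sample logistic fit to expected cell probabilities, with 1:5 matching and pre- and post-index diagnoses pooled, gives these adjusted ORs:

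| BPD OR, psychiatric OR on covariate | 30% pre-index | 50% pre-index | 70% pre-index |
|---|---|---|---|
| 1.5, 1.5 | 1.98 | 1.97 | 1.96 |
| 1.5, 2 | 1.97 | 1.94 | 1.92 |
| 2, 2 | 1.94 | 1.90 | 1.86 |
| 2, 3 | 1.90 | 1.83 | 1.77 |

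Comparator prevalences of 5% and 10% give the same values to within 0.001. When the outcome is limited to post-index diagnoses in people with none in the prior three years, the same inputs return 2.00.

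**The case against.** - **Order alone does not cause bias.** The back disorder must also have altered the covariate by the index date. If it has not, the factor is exactly 1. The documents give no figure for this, so the bias may be negligible. This stands, and the size must be given as a range that reaches almost to no bias.
- **The covariates may still be confounders.** Socioeconomic position persists, so index-date income partly stands in for earlier income, which can be a genuine confounder. The illustration assumes no confounding and so counts only the cost of adjusting. This stands, and it is why the covariates should be redated rather than dropped.
- **CCI is the weakest case.** It is the only one of these covariates with an explicit date, but the mechanism above is argued for income and marital status. This stands: CCI shares the timing problem, and no more than that is shown.
- **Scope.** The primary outcome is a prevalence comparison in an age- and sex-matched cohort, and crude risks are planned. These are untouched, as are post-index diagnoses if all covariates are taken at index. This stands.
- **Earlier dating is not a complete cure.** The definition does not require a first diagnosis, and it includes F70-F79, F80-F89 and F90-F98. Childhood-onset and recurrent disorders can precede even covariates taken three years earlier. This stands as a limit of the fix.

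None of these points removes the timing fault or supplies the missing dates.

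**Conclusion.** The concern holds for the adjusted Study 1 ORs. The plan's own definitions place index-date covariates after every pre-index psychiatric diagnosis, and nothing in Study 1 corrects for it. Under the assumed inputs a true OR of 2.00 becomes about 1.77 to 1.98 for one covariate. The shift is toward the null provided that BPD and psychiatric illness push the covariate in the same direction without interaction.

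A reader might infer more than this. The documents do not show that the adjusted ORs are biased downward, or by a known amount: that depends on effects on income and marital status which they do not report. Nor do they show that these variables are not confounders, that half of the diagnoses fall in the pre-index half of the window, or that the prevalence comparison itself is invalid. The point is a worthwhile, inexpensive improvement to the adjusted analysis.

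**What to change.** 1. **Date the covariates.** For each patient, and for matched controls using the matched patient's index date, take income, education and marital status at or before the opening of the outcome window. Marital status can be taken on the opening date for everyone. Income from the last full calendar year before the window is available for index years 2011-2014 (income years 2007-2010). For index year 2010 that year would be 2006, which is not retrieved. Use 2007 and state that it overlaps the window, so the problem is reduced rather than removed for those patients. State the date of CCI for controls.
2. **Show three models side by side:** age and sex; then adding the redated socioeconomic covariates; then also adding CCI. Do this for BPD overall and for IBD, DBD and UBP.
3. **Add a sensitivity analysis.** Split psychiatric diagnoses into before and after index, as Study 2 already does. Fit the model with index-date covariates to post-index diagnoses in people with none in the three years before.

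The cost is new wording, other years of variables already planned for retrieval, and a few additional models. The downside is that older covariates leave slightly more residual confounding for post-index diagnoses. Education may be incomplete in the youngest adults, and recurrent or childhood-onset disorders may still precede the covariates.

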Hypothesis: 1) Psychiatric comorbidity affects type of treatment in BPD patients and 2) psychiatric comorbidity affects type of treatment in subgroups of BPD.

Design and study population: The study will be a nationwide register-based cohort study. The study population consists of patients with BPD and in the sub-analysis the study population consists of patients with BPD and psychiatric comorbidity.

Procedure: BPD patients will be identified via the DNPR. Surgical treatment will be defined as the presence of any procedure code for back surgery retrieved from DNPR (NOMESCO: KNA-W)³⁴⁻⁴⁰. Pharmacological treatment of BPD will be defined as any treatment with the following drugs: NSAID (ATC: N01A*), acitomenophen (ATC: N02BE01), opioids (N02A*), antiepileptica (ATC: N03A) and tricyclic antidepressants (ATC: N06AA)¹³ identified using the Register of Medicinal Products Statistics⁷. Data on other types of treatment (defined as any treatment not surgical or pharmacological) such as physiotherapist, psychologist, chiropractor or occupational therapist (covered via tax-funded health insurance) will be obtained via The Danish National Health Insurance Service Register (SSR)³⁷. All BPD treatment-related information will be retrieved up to three years after the date of BPD diagnosis.

Information on somatic comorbidity for calculation of Charlson Comorbidity index³⁹ (CCI) at time of BPD diagnosis, will be retrieved from the DNPR. Data on psychiatric comorbidity will be identified using NPD-Psych. Information on psychiatric comorbidity will be used to define whether each patient had a psychiatric diagnosis prior to BPD diagnosis, after BPD diagnosis or no psychiatric diagnosis. If a psychiatric diagnosis occurs both prior to and after BPD diagnosis, the patient will be defined as having a psychiatric comorbidity prior to BPD diagnosis.

Information on marital status, vital status, and immigration status will be retrieved from the Civil Registration System (CPR)³⁵. Patients that are not alive or have emigrated within three years after BPD diagnosis are considered lost to follow-up and excluded from the cohort. Descriptive data on the socioeconomic status, education level and equivalent available income will be retrieved from Statistics Denmark³⁸. All data comprising each variable will be retrieved from 1th of January 2007 to 31th of December 2017 (three years before and after study period).

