Measures of outcome: The outcome is type of treatment for BPD (surgical, pharmacological and other types of treatment)

Statistics: We will use Fisher's exact test and t-test to compare patients' baseline characteristics with 95% confidence intervals (CI) and p-values. For each treatment type we will use logistic regression model to investigate differences in outcome distribution between patients with and without psychiatric comorbidity. The logistic regressions will be performed with 95% CI adjusted for the following confounders: age, sex, CCI, level of education, equivalent available income, type of BPD (IBD, DBD or UBP) and marital status.

Study 3) Effect of psychiatric comorbidity in pharmacological treatment of BPD.

Aim: 1) To compare dosages of pharmacological treatment in BPD patients with and without the presence of psychiatric comorbidity in a nationwide Danish cohort study in 2010-2014. 2) To compare high vs. low dosages of pharmacological treatment for BPD in patients with BPD and psychiatric comorbidity.

Hypothesis: 1) Patients with BPD and psychiatric comorbidity are prescribed a higher dosage of pain medication for BPD compared with BPD patients without psychiatric comorbidity. 2) BPD patients with a psychiatric comorbidity with a high (defined as above the 50th percentile) vs. low (defined as below the 50th percentile) dosage of pain medication are also prescribed higher dosages of psychiatric medication.

Design and study population: The study will be a nationwide register-based cohort study. The study population consists of patients with BPD that received pharmacological treatment for BPD. In the secondary analysis the study population consists of patients with BPD and a psychiatric comorbidity, who received pharmacological treatment for BPD.

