Procedure: BPD patients will be identified via the DNPR. Pharmacological treatment of BPD will be defined as any treatment with the following drugs: NSAID (ATC: N01A*), Acitomenophen (ATC: N02BE01), Opioids (N02A*)¹³. Pharmacological treatment for psychiatric comorbidity will be defined as any treatment with the following drugs: Antipsychotics (ATC:N05A), Antidepressants (ATC: N06A), Selective Serotonin Reuptake Inhibitors (SSRI) (ATC: N06AB), and anxiolytics (ATC: N5B*)⁴¹. Pharmacological treatment that can be used in the treatment of both BPD and psychiatric disorders will be defined as any treatment with the following drugs: Antiepileptics (ATC: N03A) and Tricyclic antidepressants (ATC: N06AA). All data on pharmacological treatment will be identified using the Register of Medicinal Products Statistics⁷. From time of BPD diagnosis and the following three years, pharmacological treatment for both somatic illness and psychiatric comorbidity in Daily Defined Dosage (DDD) per year will be calculated⁴².

Information on somatic comorbidity for calculation of Charlson Comorbidity index³⁹ (CCI) at time of BPD diagnosis, will be retrieved from the DNPR. Data on psychiatric comorbidity will be identified using NPD-Psych. Information on marital status, vital status, and immigration status will be retrieved from the Civil Registration System (CPR)³⁵. Patients that are not alive or have emigrated within three years after BPD diagnosis are considered lost to follow-up and excluded from the cohort. Descriptive data on the socioeconomic status, education level and equivalent available income will be retrieved from Statistics Denmark³⁸. All data comprising each variable will be retrieved from 1th of January 2007 to 31th of December 2017 (three years before and after study period).

Measures of outcome: Primary outcome is pharmacological treatment in DDDs defined as high (above the 50th percentile and low (below the 50th percentile) of pain medication. Secondary outcome is psychiatric medication in BPD patients with psychiatric comorbidity in DDD's defined according to high (above the 50th percentile) and low (below the 50th percentile) dosages of pain medication.

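### Study 3 codes anxiolytics as `N5B*`, which matches no code in the plan's own ATC format; correct it and check every drug code, including NSAID `N01A*`, before extraction

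*Combined protocol and SAP*

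**What the plan says.** The Study 2 Procedure gives the drug definition as a list: "Pharmacological treatment of BPD will be defined as any treatment with the following drugs", followed by "NSAID (ATC: N01A*), acitomenophen (ATC: N02BE01), opioids (N02A" with a wildcard, and then antiepileptics (`N03A`) and tricyclics (`N06AA`). The Study 2 outcome is the broad treatment type: "The outcome is type of treatment for BPD (surgical, pharmacological and other types of treatment".

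The Study 3 Procedure repeats the first three classes with the same codes: "NSAID (ATC: N01A*), Acitomenophen (ATC: N02BE01), Opioids (N02A". It then lists the psychiatric drugs: "Antipsychotics (ATC:N05A), Antidepressants (ATC: N06A), Selective Serotonin Reuptake Inhibitors (SSRI) (ATC: N06AB" and, last, "and anxiolytics (ATC: N5B", with a wildcard after the B. Antiepileptics and tricyclics form a third, dual-use group.

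These lists are used as definitions elsewhere in Study 3:
- The study population is limited to back pain patients given drugs for back pain (Design and study population).
- The primary outcome is pain-drug DDDs split at the median, and the secondary outcome is psychiatric-drug DDDs (Measures of outcome).
- Use of psychiatric drugs is an adjustment covariate in the first Cox analysis (Statistics).

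The ATC/DDD index is cited as reference 42. Its contents are not reproduced.

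**The concern.** In a register study the code list decides which records are pulled. A code that matches nothing leaves its class empty. If the psychiatric codes are pooled into one search, the other codes still return records, so the gap need not show.

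For anxiolytics, two parts of Study 3 are exposed. The secondary outcome would omit every anxiolytic dose. The covariate would put anxiolytic-only patients in the group without psychiatric drugs, so adjustment for that factor in the main comparison would be incomplete.

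The NSAID code raises a different question. It is a valid-looking code that appears identically in both studies, so comparing the two lists would not reveal a slip if there were one. More depends on it, because the pain-drug list fixes both who enters Study 3 and the dose that is split.

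**Working it through.** **Step 1. Format of every code.** Inputs are the nine distinct codes in the Study 2 and Study 3 Procedures. The test is whether each begins with a letter, two digits and a letter.

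| Class | Code | Study | Fits |
|---|---|---|---|
| NSAID | `N01A*` | 2, 3 | yes |
| Acetaminophen | `N02BE01` | 2, 3 | yes |
| Opioids | `N02A*` | 2, 3 | yes |
| Antiepileptics | `N03A` | 2, 3 | yes |
| Tricyclics | `N06AA` | 2, 3 | yes |
| Antipsychotics | `N05A` | 3 | yes |
| Antidepressants | `N06A` | 3 | yes |
| SSRI | `N06AB` | 3 | yes |
| Anxiolytics | `N5B*` | 3 | **no** |

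Eight of nine fit.

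**Step 2. What a literal search returns.** There are 26 × 100 × 26 = 67,600 possible stems of the form letter, two digits, letter. None starts with `N5B`, because the third character must be a digit. Exactly one starts with `N05B`. So `N5B*` returns nothing, and restoring one zero gives a well-formed code next to the antipsychotic code `N05A`.

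**Step 3. Effect on the secondary outcome.** Let a be the anxiolytic share of a group's psychiatric DDDs. The extracted total is (1 − a) times the true total. For a ratio of mean DDDs between the high and low pain-dose groups, observed ratio = true ratio × (1 − a_high)/(1 − a_low). The level is always too low when a > 0. The ratio is distorted only if the shares differ, and the direction depends on which is larger. The documents give no value for a.

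**Step 4. Effect on the covariate.** If the covariate is built from the psychiatric list, the patients misclassified are those with an anxiolytic and none of the other psychiatric codes. If the dual-use group also counts, fewer are affected. The documents do not size this group.

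**Step 5. The NSAID code.** `N01A*` passes step 1, so a format check cannot show it to be wrong. What depends on it differs by study:
- Study 3: NSAIDs are one of three pain-drug classes. If the code missed them, NSAID-only patients would leave the population and NSAID doses would be absent from the median split.
- Study 2: NSAIDs are one of five classes in an any-drug definition, so only patients with none of the other four would be misclassified.

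A conditional illustration for Study 2 follows. It applies only if a look-up shows that the code misses NSAIDs, and every rate in it is an assumption. Take true treated shares of 85% with and 80% without psychiatric comorbidity. The odds ratio is (0.85/0.15)/(0.80/0.20) = 1.42. With NSAID-only shares s1 and s0 among the treated, the observed shares are 0.85(1 − s1) and 0.80(1 − s0).

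| s1, s0 | Observed shares | Odds ratio |
|---|---|---|
| 0, 0 | 0.850, 0.800 | 1.42 |
| 10%, 10% | 0.765, 0.720 | 1.27 |
| 20%, 20% | 0.680, 0.640 | 1.20 |
| 10%, 20% | 0.765, 0.640 | 1.83 |
| 20%, 10% | 0.680, 0.720 | 0.83 |

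The result runs from no change to a reversal. This is a reason to do the look-up; it does not estimate bias in this study.

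**The case against.** The strongest reply is that this is a typing slip in a PhD project proposal. Each code stands beside a class name, so the intended drugs are clear, and a programmer who saw an empty anxiolytic class would add the zero. The slip occurs once, in Study 3, in psychiatric rather than pain drugs. It touches a secondary outcome and one covariate, not the primary outcome itself. All of that stands, and it keeps the point small. It does not remove it: the plan describes no check of codes against labels, and a pooled search would not show the empty class.

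A reader might go further and infer that `N01A*` is the wrong group for NSAIDs, so that both studies lose a main pain-drug class. The documents do not support that. The code is well formed, the two Procedures agree on it, and the index that would settle the matter is cited but not reproduced. Nor do the documents say how many patients use NSAIDs, so the weight of the class cannot be judged from them. Naming a replacement code would have the same weakness.

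**Conclusion.** The anxiolytic code in Study 3 is wrong as written. Against the plan's own format it matches no code, so literal extraction would return no anxiolytics, understate psychiatric-drug DDDs, and code anxiolytic-only users as having no psychiatric drugs in the main Cox model. This assumes that the code is run as printed and that the covariate uses the psychiatric list in the Procedure. The size cannot be given, because the documents contain no figure for anxiolytic use. That `N05B*` is what was meant is inferred from the format and should be confirmed by the listing.

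For `N01A*` the conclusion is only that it needs checking. Any loss of NSAIDs depends on a look-up not yet made. If that look-up showed an error, the consequence would be direct in Study 3 and limited in Study 2 to patients with none of the other four classes.

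**What to change.** 1. In the Study 3 Procedure, replace `N5B*` with `N05B*`.
2. Before the extraction is locked, list the substance names returned by every code in the Study 2 and Study 3 Procedures, and confirm that they match the class label under the ATC index in reference 42.
3. Include `N01A*` in that listing. If it does not return NSAIDs, correct it in both studies; if it does, record that and leave it.
4. State in the Study 3 Statistics section which codes make up the psychiatric-drug covariate.

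The cost is one code correction, one clarifying sentence and a short listing. If the data have already been extracted, add one re-pull for the codes that change.
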